3.2 Headline Analyses Prior to Database Freeze (DBF)

The following is conditional on the study not being stopped early by the interim analysis. To facilitate internal GSK decision making a data snapshot will be taken when the last subject's BAC FEV₁ data (and derived LAR endpoints) from FUV1 are available. The associated planned efficacy outputs (see Section 11.13.4-Section 11.13.16) will be produced from that (unblinded) snapshot and shared internally with the GSK study team and internal GSK governance boards/senior management. As this data snapshot will be pre-DBF its results will not be formally reported as they will be superseded by the formal end of study results. A separate reporting effort for the headline analyses will be created in the HARP system.

3.3 Safety Review Team (SRT)

Safety Review Team meetings are planned for this study as per GSKs standard pharmacovigilance policies. The SRT is expected to meet on a regular basis to review ongoing safety data, usually via TSCG (Spotfire) and standard TFLs. The SRT meetings are beyond the scope of this RAP and will be documented separately as part of their operating processes.

3.4 Final Analyses

The final planned primary analyses will be performed after the completion of the following sequential steps:

1. All subjects have completed the study as defined in the protocol i.e., once all subjects have completed the last follow-up visit or lost to follow-up.
2. All required database cleaning activities have been completed and final database release (DBR) and database freeze (DBF) has been declared by Data Management.
3. All criteria for unblinding the (remaining) randomisation codes have been met.
4. Randomisation codes have been distributed according to RandAll NG procedures.

4 ANALYSIS POPULATIONS

Population	Definition / Criteria	Analyses Evaluated
Screened	
 • Comprise of all subjects who were screened for inclusion into the study and have any value databased in the eCRF. 	
 • Study Population
Enrolled ¹	
 • Comprise of all subjects who were enrolled ie, randomised to study treatment. • Only required for 'Summary of Age Ranges' data display; necessary for disclosure purposes to EudraCT and FDAAA. 	
 • Demographics
All Subjects	
 • Comprise of all subjects who receive at least one dose of study treatment. • This population will be based on the treatment the subject actually received. 	
 • Study Population • Safety • Biomarkers
Run in failures	
 • Comprise of all subjects who were assigned a randomisation number (even if it was assigned in error) but did not receive any doses of study treatment 	
 • Study Population
Modified Intent-To-Treat (mITT)	
 • Comprise of all randomised subjects who receive at least one dose of study treatment and commence a BAC at follow-up. • This population will be based on the treatment the subject received. • Any subject who receives a treatment randomisation number will be considered to have been randomised. 	
 • Efficacy
Per-Protocol (PP)	
 • Comprise of all mITT subjects who comply with the protocol. • Protocol deviations that would exclude subjects from the PP population are defined in Section 4.1 (Protocol Deviations) and Appendix 1 (Protocol Deviation Management and Definition for Per-Protocol Population). 	
 • Efficacy
Pharmacokinetic (PK)	
 • Subjects in the 'All Subjects' Population for whom a pharmacokinetic sample is obtained and analysed. 	
 • Pharmacokinetic
Sputum Producers (Sputum)	
 • Subjects in the 'All Subjects' Population for whom a viable pre- or post-challenge sputum sample is obtained (at Screening). 	
 • Sputum Biomarkers
Interim Analysis (IA1)	
 • Subjects contributing data points used in an Interim analysis (Note: The planned headline analysis is not counted as an interim analysis) 	
 • Study Population

Population	Definition / Criteria	Analyses Evaluated
	
 If more than one interim analysis occurs then a separate population will be created for each subsequent interim, using sequential names (e.g. IA2, IA3, etc) 	

NOTES :

- Please refer to [Appendix 13](#): List of Data Displays which details the population to be used for each display being generated.
- If the 'All Subjects' Population contains the same subjects as 'Enrolled' Population, the 'Enrolled' Population will be dropped and 'All Subjects' used instead.

4.1 Protocol Deviations

- Important protocol deviations (including deviations related to study inclusion/exclusion criteria, conduct of the trial, patient management or patient assessment) will be summarised and listed.
- Important deviations which result in exclusion from the analysis population will also be summarised and listed (please refer to [Appendix 1](#): Protocol Deviation Management and Definitions for Per Protocol Population).
- Protocol deviations will be tracked by the study team throughout the conduct of the study in accordance with the Protocol Deviation Management Plan.
 - Data will be reviewed prior to unblinding and freezing the database to ensure all important deviations and deviations which may lead to exclusion from the analysis are captured and categorised on the protocol deviations dataset.
 - This dataset will be the basis for the summaries and listings of protocol deviations.
- A separate summary and listing of all inclusion/exclusion criteria deviations will also be provided. This summary/listing will be based on data as recorded on the inclusion/exclusion page of the eCRF.

5 CONSIDERATIONS FOR DATA ANALYSES AND DATA HANDLING CONVENTIONS

Table 3 provides an overview of appendices within the RAP for outlining general considerations for data analyses and data handling conventions.

Table 3 Overview of Appendices

Section	Component
11.1	Appendix 1 : Protocol Deviation Management and Definitions for Per Protocol Population
11.2	Appendix 2 : Assessment Windows
11.3	Appendix 3 : Treatment States and Phases
11.4	Appendix 4 : Data Display Standards & Handling Conventions
11.5	Appendix 5 : Derived and Transformed Data
11.6	Appendix 6 : Premature Withdrawals & Handling of Missing Data
11.7	Appendix 7 : Values of Potential Clinical Importance
11.8	Appendix 8 : Multicentre Studies
11.9	Appendix 9 : Examination of Covariates, Subgroups & Other Strata
11.10	Appendix 10 : Multiple Comparisons & Multiplicity
11.11	Appendix 11 : Model Checking and Diagnostics for Statistical Analyses.
11.12	Appendix 12 : Abbreviations and Trade Marks
11.13	Appendix 13 : List of Data Displays

6 STUDY POPULATION ANALYSES

6.1 Overview of Planned Analyses

The study population analyses will be based on the ‘All Subjects’ Population, unless otherwise specified.

Table 4 provides an overview of the planned study population analyses, with full details of data displays being presented in [Appendix 13](#): List of Data Displays.

Table 4 Overview of Planned Study Population Analyses

Endpoint / Parameter / Display Type	Data Displays Generated		
	Table	Figure	Listing
Subject Disposition			
Subject Disposition	Y		
Screening Status and Reasons for Screen Failure	Y		Y
Subjects by Country and Centre	Y		
Subjects by Country and Centre and Allergen Exposure Strata	Y		
Reasons for Subject Withdrawal			Y
Subjects for Whom the Treatment Blind was Broken			Y
Planned and Actual Treatments			Y
Protocol Deviations			
Important Protocol Deviations	Y		Y ^[1]
Subjects with Inclusion/Exclusion Criteria Deviations			Y
Populations Analysed			
Study Populations and Exclusions	Y		
Subjects Excluded from Any Population			Y
Demographic and Baseline Characteristics			
Demographic Characteristics	Y		Y
Summary of Age Ranges	Y		
Race and Racial Combinations	Y		Y ^[2]
Skin Prick Test at Screening	Y		Y
Medical Conditions and Prior and Concomitant Medications			
Current/Past Medical Conditions	Y		Y
Concomitant Medications	Y		Y
Exposure and Treatment Compliance			
Exposure to Study Treatment			Y

NOTES :

- Y = Yes display generated.

[1] Listing also includes analysis population exclusions.

[2] Listing of race.

7 PRIMARY STATISTICAL ANALYSES

7.1 Efficacy Analyses

7.1.1 Overview of Planned Efficacy Analyses

The primary efficacy analyses will be based on the PP population, unless otherwise specified. As a potential sensitivity analysis the final primary analysis model structure (derived using the PP population) may also be run using the mITT population (conditional on the PP and mITT populations differing).

Table 5 provides an overview of the planned efficacy analyses, with full details of data displays being presented in [Appendix 13: List of Data Displays](#).

Table 5 Overview of Planned Efficacy Analyses

Endpoint	Absolute							
	Stats Analysis			Summary		Individual		
	T	F	L	T	F	F	L	
LAR								
Min and WM FEV ₁ absolute change from saline at Week 9 (FUV1)	Y	Y	Y	Y	Y	Y	Y	

NOTES :

- T = Table, F = Figure, L = Listing, Y = Yes display generated.
- Stats Analysis = Represents TFL related to any formal statistical analyses (i.e. modelling) conducted.
- Summary = Represents TFL related to any summaries (i.e. descriptive statistics) of the observed raw data.
- Individual = Represents FL related to any displays of individual subject observed raw data.

7.1.2 Planned Efficacy Statistical Analyses

Primary Statistical Analyses
Endpoint(s)

 • LAR: minimum <change from saline baseline> FEV₁ between 4-10 hours following allergen challenge 1 week after treatment i.e. FUV1. • LAR: weighted mean of <change from saline baseline> FEV₁ between 4-10 hours following allergen challenge 1 week after treatment i.e. FUV1. 
Note: Text in <> added for clarity, since the wording in the protocol and objectives is familiar to clinical experts in the field, but may be confusing given there are also absolute FEV1 values measured at those times too.
 
 • The “raw” data (replicate (absolute) FEV1 values transcribed into the eCRF) require processing before the Primary analysis. Each planned timepoint may be associated with replicate FEV1 values, which need to be condensed down into a single value (giving a single FEV1 value per timepoint per subject; the timepoints determine how the data are condensed, i.e. some timepoints use the minimum of the replicates others use the maximum). In addition the Screening Visit 2 Incremental BAC challenge may also contain additional FEV1 values relating to the selection procedure for the bolus BAC concentration. Such FEV1 values are not used in the statistical analyses (subjects may differ in the amounts of additional FEV1 data to be excluded). Once the single time profile of absolute FEV1 values is available per subject the Saline baseline is subtracted from each to leave a time profile of change from saline baseline FEV1 values. The minimum and weighted means endpoints are derived from this change from saline baseline time profile. Further details are given in Section 11.5.4. • Any transformation of a response variable is also expected to be applied to the corresponding baseline variable. Final decisions on transformations will be based on the observed data and model diagnostics • Any observations with missing model covariates (e.g. baseline) would be excluded from the model fitting process (i.e. also excluding the record from any centering of covariates)
Model Specification

 • Each endpoint will be analysed separately using a Bayesian Mixed effects model fitted within Proc MCMC in SAS using the following approach: • Assume equal variances across treatment arms and use a pooled estimate of residual variability (Note: if the posterior predictive distributions produced to support the interim analysis suggest this assumption may be invalid then the modelling approach may be modified to estimate separate variance terms for each treatment arm). • Step 1: Fit all three of the following models (report output from each model in the same listing – along with the DIC values and changes in DIC values between models). Using a combination of changes in the DIC criteria, and expert judgment (see Section 11.9.1), select a single model. 
 • M1: Intercept + Centre + Treatment + Allergen Exposure + Treatment*Allergen Exposure + Baseline • M2: Intercept + Centre + Treatment + Allergen Exposure + Baseline • M3: Intercept + Centre + Treatment + Baseline • See Section 11.4.2 for Baseline definitions (Screening visit 2 BAC endpoint).

Primary Statistical Analyses

Where in each of the models (M1, M2 and M3) the effects are:

Type	Name (#Levels)	Parameters	Prior(s)
Fixed Categorical	Intercept (1)	#1 Intercept	N (0, Var=1E6)
	Treatment (2)	#1 Placebo	N (0, Var=1E6)
		#2 20ng	n/a (constraint = 0)
	Allergen Exposure (2)	#1 Presumed	N (0, Var=1E6)
		#2 Unknown	n/a (constraint = 0)
	Treatment * Allergen Exposure (4)	#1 Pbo*P	N (0, Var=1E6)
		#2 Pbo*U	n/a (constraint = 0)
		#3 20ng*P	n/a (constraint = 0)
		#4 20ng*U	n/a (constraint = 0)
Fixed Continuous*	Baseline	Baseline slope	N(0, Var=1E6)
Random	Centre (planned 6 centres)	Separate value per contributing centre sampled as i.i.d $\sim N(0, \sigma_{Centre}^2)$	$\sigma_{Centre}^2 \sim \text{Gamma}(\text{Shape}=0.048, \text{Scale}=0.830)$ Weakly informative prior based on 6x in-house GSK datasets – same prior for both endpoints Δ

*=Centre covariates prior to fitting model (do not use observations that will not contribute to the planned model when centering) and if applicable the centering is to occur after any transformations have been applied

Δ =If chain is not mixing (i.e. sticking at values close to zero) an additional mixture prior may be considered to act as a lower boundary constraint, or the centre term excluded from the model.

- Step 2 (optional): Explore adding other covariate terms to the Step 1 model (for example, but not limited to, Age, Gender, Dose per kg, Blood eosinophil levels). Use expert judgment and changes in DIC to determine final model to take to Step 3. Include any Step 2 models in the listing output and add the associated DIC / changes in DIC values to those produced in Step 1.
- Step 3: For the finally selected model use appropriate combinations of the model parameters (back transforming the combination if necessary) to obtain posterior distributions for the quantities of interest described in the Model Results Presentation. Binary flag variables can be used to evaluate the probability statements, by tracking the instances of the desired event happening over each MCMC iteration and taking the mean of the flag variable as the probability.

For example, if Model 3 is selected then the posterior distribution for the Placebo can be

Primary Statistical Analyses

obtained from adding model parameters Intercept + Treatment[#1] Note: The baseline term is centered and drops out of the expression since it is evaluated at its centered mean of zero; similarly the random centre effect also has mean zero.

The treatment difference (Active – Placebo) would be –Treatment[#1] because the Treatment[#2] parameter is constrained to be zero and the other model terms cancel out.

The Percentage attenuation would be $100 * (1 - (\text{Intercept} / (\text{Intercept} + \text{Treatment}[\#1])))$

The SAS syntax for setting up indicator flags to obtain the probability of any percentage attenuation is Myflag = (pctann > 0); where pctann is the variable storing the Percentage attenuation.

Programming technical note(s): i) Use of flag variables may result in several error/warning messages in the SAS log (for example, but not limited to, warnings about large autocorrelation and/or zero variance); which should be reviewed but may be safely discounted – if in doubt consult the study statistician. ii) To facilitate summary outputs where results from multiple models are displayed simultaneously (large) intermediate datasets from Proc MCMC may need to be stored to ensure consistency (i.e. no differences due to simulation error between model re-runs). Suitable naming conventions should be used to label these files which group related items together.

- The randomization seed used in PROC MCMC should itself be generated with an element of randomness - but there is no need to formally document this process (e.g. using Excel function RANDBETWEEN [1,9999999] and copying the result into the SAS code)
- In addition posterior probabilities relating to differences and/or percentage attenuations for other cut-points (which may be determined upon inspection of the data, or from developing business requirements), may also be produced.

Model Checking & Diagnostics

- Refer to [Appendix 11: Model Checking and Diagnostics for Statistical Analyses](#).

Model Results Presentation

- Point estimates (median values of the posterior distributions), the standard deviation of the posterior distribution (SDs) and 95% & 70% equi-tailed credible intervals will be presented for each treatment together with estimated treatment differences relative to Placebo and their corresponding 95% and 70% credible intervals. The treatment differences will also be expressed as percentage attenuations relative to Placebo (and posterior distribution of the percentage attenuation obtained). The posterior probability of any treatment reduction (any percentage attenuation) will also be displayed, along with the posterior probability of the percentage attenuation exceeding the corresponding AZ point estimate (27% attenuation for WM LAR and 18% attenuation for Minimum LAR) ([Leaker, 2012](#)).
- Plots of the point estimates for the treatment effects (median values of the corresponding posterior distributions) and 95% & 70% credible intervals from the model will be generated for each treatment. Additionally, plots of differences and 95% & 70% credible intervals for the comparison of GSK2245035 vs Placebo may be generated (for the absolute difference and percent attenuation representations).
- Note: In the event that Model M1 is selected as final (or the final model includes an interaction

Primary Statistical Analyses			
term involving treatment and another fixed categorical covariate) the outputs should be adjusted accordingly to present treatment comparisons within each level of the covariate. If the interaction term involving treatment is with a continuous covariate the mean value of the covariate should be used and the outputs clearly labeled that the prediction is made at the specified covariate value.			
Sensitivity and Supportive Statistical Analyses			

 A scatterplot of each subject's two derived primary endpoints (each endpoint is an axis) – with appropriate identification of subjects belonging to the four distinct treatment & allergen exposure combinations. Include i) the (overall) Pearson correlation coefficient and optionally ii) corresponding density estimates for each combination and axis as plot margin panels As an informal check the weakly informative prior on the variance component of the centre effect may be replaced by a non-informative prior and the treatment estimates compared, provided both models converge, to confirm the prior is not more informative than was intended (outputs from this check do not need to be formally reported) Informative priors based on AZ published data/effect sizes may be explored for the treatment terms. Priors that need to be modified in models M1, M2 and M3 are indicated below (Priors for WM LAR endpoint only, and analysis would only be required for PP population): 			
Type	Name (#Levels)	Parameters	Prior(s)
Fixed Categorical	Intercept (1)	#1 Intercept	N (-0.7081, Var=0.4472^2 / 26)
	Treatment (2)	#1 Placebo	N (-0.2619, Var=0.4472^2 * (1/25 – 1/26))
		#2 20ng	n/a (constraint = 0)

 A sensitivity analysis applying the final model to the mITT population may be performed Exploration of the relationship between treatment effect sizes and (potential) sub-populations based on eosinophil levels in blood: A model building exercise would take place using a similar strategy as that used to explore the importance of allergen exposure status. However, the base model will start with the simplifying assumption that allergen exposure is not necessary (i.e. use the M3 form of model). The base model will be compared to the fit of a model containing an additional term for the (log transformed if necessary and centered) absolute blood eosinophil from the Baseline visit (SV2, fitted as a continuous covariate). This is similar to model form M2 but with the continuous covariate taking the place of the allergen exposure term. Additionally the benefit of adding a term for the interaction between treatment and this continuous covariate will be explored (similar to the M1 form). If any model terms involving blood eosinophils are included in the model it will be used to predict the mean response for each treatment arm using the following blood eosinophil levels (values presented here may require transformation so they are incorporated into the model prediction on the appropriate scale): 100 cells/mL and 200 cells/mL. Also the treatment difference at each of those eosinophil levels should be evaluated. Non-informative priors would be used for the parameters representing these additional term(s). To produce the descriptive summary tables the blood eosinophil variable will be grouped and summarized by the categories described in Section 11.9.1. Note: If data permit the allergen exposure status may also be added to the model (although there may not be sufficient subjects to estimate the required number of model 			

Primary Statistical Analyses

parameters; especially when trying to estimate the multi-way interactions involving treatment, allergen exposure and eosinophil levels).

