Hypothesis	
 No formal statistical hypotheses are to be tested. The primary study objective will assess the effect of a weekly dose of 20ng GSK2245035 vs Placebo by precision estimation and credible intervals to estimate the magnitude of underlying effect sizes. A Bayesian approach will be utilised to obtain the posterior distribution for the mean treatment effects for the endpoints in the study (e.g. posterior distributions for percentage attenuation for the endpoint LAR: minimum FEV₁ between 4-10 hours following allergen challenge one week after treatment.). Other objectives will assess other pharmacodynamic effects and safety and tolerability of GSK2245035.

Overview	Key Elements of the RAP
Primary Analyses	
Statistical models will be fitted separately to each LAR endpoint (weighted mean and minimum FEV₁ change from saline at the FUV1 visit). These parameters will be analysed using a Bayesian version of a mixed effects model (centre as a random effect, and baseline as a covariate). A series of nested models will be fitted to determine if the allergen strata (and interaction with treatment) are necessary.The principal inferences are expected to come from models with non-informative priors. Sensitivity analyses using informative priors based on AZ data may also be attempted.
Secondary Analyses	
Statistical models will be fitted separately to each EAR endpoint (weighted mean and minimum FEV₁ change from saline at the FUV1 visit). These parameters will be analysed using the same modelling approach as the Primary analysis.

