- Active: Sample Mean Vector $\begin{bmatrix} \bar{x}_1 & \bar{x}_2 \end{bmatrix}_{Act}$ Sample VCV $\begin{bmatrix} S_{WM}^2 & S_{WM}S_{Min} \\ S_{WM}S_{Min} & S_{Min}^2 \end{bmatrix}_{Act}$

Interim Analyses to estimate end of study success
--

- In the statistical model fitted to the WM endpoint the priors are:

$$\hat{\mu}_{P,WM} \sim N\left(\bar{x}_{1,Pbo}^{WM}, \frac{S_{WM,Pbo}^2}{Nrem_{Pbo}}\right), \quad \hat{\mu}_{A,WM} \sim N\left(\bar{x}_{1,Act}^{WM}, \frac{S_{WM,Act}^2}{Nrem_{Act}}\right)$$

- In the statistical model fitted to the Min endpoint the priors are

$$\hat{\mu}_{P,Min} \sim N\left(\bar{x}_{2,Pbo}^{Min}, \frac{S_{Min,Pbo}^2}{Nrem_{Pbo}}\right), \quad \hat{\mu}_{A,Min} \sim N\left(\bar{x}_{2,Act}^{Min}, \frac{S_{Min,Act}^2}{Nrem_{Act}}\right)$$

Step 3: Fit model and flag success or failure
--

- To facilitate easy use of the prior distributions a re-parameterized version of Primary analysis Model M3 can be used (Intercept term removed and the zero constraint on the 2nd treatment level removed).
- Separate models will be fitted to each of the endpoints (WM and Min)
- If the posterior probability that $\hat{\mu}_P < \hat{\mu}_A$ exceeds 0.7 (using the informative prior from the ith MCMC iteration) then the ith MCMC iteration is flagged as resulting in a successful end of study result.
- The overall probability of success is the number of successful MCMC iterations / total number of MCMC iterations

Technical details for deriving the individual tables contributing to [Table 2](#)

To determine the probability of success in the presence of non-LAR responders simulations were performed for each possible combination of number of available placebo subjects (n) and number showing no LAR response (r) using the AZ point estimates as the true percentage attenuation (separate procedure for each of the primary endpoints):

Let K represent the number of subjects per arm to be evaluated with each value of K producing a different table and K ranging from 21 to 30 by 1.

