2.4.	mITT	EFF_T2	Summary of Posterior Distributions and Posterior Probability statements - Bronchial Allergen Challenge Minimum and Weighted Mean LAR Absolute Change from Saline at Week 9 (FUV1)	Conditional on PP and mITT populations differing. As per PP equivalent	SAC 1

Efficacy: Tables					
No.	Population	IDSL / TST ID / Example Shell	Title	Programming Notes	Deliverable [Priority]
2.5.	PP	EFF_T2	Sensitivity Analysis: Summary of Posterior Distributions and Posterior Probability statements - Bronchial Allergen Challenge Minimum and Weighted Mean LAR Absolute Change from Saline at Week 9 (FUV1) using Informative Priors	Sensitivity analysis: Display priors as footnotes / or as appropriate in the output	HR 2, SAC 2
2.6.	PP	EFF_T2	Sensitivity Analysis: Summary of Posterior Distributions and Posterior Probability statements - Bronchial Allergen Challenge Minimum and Weighted Mean LAR Absolute Change from Saline at Week 9 (FUV1) using Blood Eosinophil level as a covariate	Modify Table structure to also indicate which value of esoinophils the prediction/item is associated with	SAC 2
2.7.	PP	EFF_T2	Summary of Repeated Measures Posterior Distributions and Posterior Probability statements - Bronchial Allergen Challenge Minimum and Weighted Mean LAR Absolute Change from Saline	As per single timepoint version (the Planned Time column should contain the Visit and Timepoints within visits, e.g. FUV1, FUV2)	SAC 2
2.8.	miITT	EFF_T2	Summary of Repeated Measures Posterior Distributions and Posterior Probability statements - Bronchial Allergen Challenge Minimum and Weighted Mean LAR Absolute Change from Saline	Conditional on PP and miITT populations differing. As per PP equivalent version	SAC 2
2.9.	PP	EFF_T2	Sensitivity Analysis Summary of Repeated Measures Posterior Distributions and Posterior Probability statements - Bronchial Allergen Challenge Minimum and Weighted Mean LAR Absolute Change from Saline using Blood Eosinophil level as a covariate	As per PP equivalent version but modify Table structure to also indicate which value of esoinophils the prediction/item is associated with	SAC 2
EAR					
2.10.	PP	EFF_T1	Summary of Bronchial Allergen Challenge Minimum and Weighted Mean EAR Absolute Change from Saline by Visit	As per LAR equivalent	SAC 1
2.11.	PP	EFF_T1	Sensitivity Analysis: Summary of Bronchial Allergen Challenge Minimum and Weighted Mean EAR Absolute Change from Saline by Visit and Blood Eosinophil Level	As per LAR equivalent	SAC 2

Efficacy: Tables					

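### The AZ-based prior on the weighted mean LAR treatment difference has a variance 51 times too small, so that sensitivity analysis returns a benefit whatever the data show

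*SAP*

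**What the plan says.** The primary models M1 to M3 in SAP 7.1.2 set the 20 ng level of Treatment to zero. The Intercept is therefore the active-arm mean, and Intercept + Treatment[#1] is the placebo mean. Step 3 confirms the meaning of the treatment parameter: "The treatment difference (Active – Placebo) would be –Treatment[#1] because the Treatment[#2] parameter is constrained to be zero".

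Among the supportive analyses, the SAP states: "Informative priors based on AZ published data/effect sizes may be explored for the treatment terms". This applies to weighted mean (WM) LAR in the Per-Protocol population. Two priors replace the non-informative ones:

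- Intercept: "N (-0.7081, Var=0.4472^2 / 26"
- Treatment[#1]: "N (-0.2619, Var=0.4472^2 * (1/25 – 1/26"

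No covariance between the two is given. Other terms, including the treatment-by-exposure interaction in M1, keep their N(0, 1E6) priors.

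The result goes to Table 2.5 (SAP 11.13.5), a priority 2 output for both the headline and the final deliveries. Its programming note reads: "Sensitivity analysis: Display priors as footnotes / or as appropriate in the output".

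**The concern.** A difference between two independently estimated means is less certain than either mean, so its variance is the sum of their variances. The SAP subtracts them. The subtraction appears deliberate: with independent priors it makes Intercept + Treatment[#1] have variance 0.4472²/25, which is what a placebo mean based on 25 subjects should have. It achieves this by leaving almost no prior uncertainty on the treatment difference, the one quantity the analysis is meant to examine.

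A sensitivity analysis should show how far conclusions move when outside evidence is added. If the prior fixes the difference, the output repeats the AZ result and the trial's data hardly matter. SAP 3.2 sends headline outputs to the study team, governance boards and senior management for internal decisions. If Table 2.5 is produced, they would see near-certain benefit even after a clearly unfavourable result.

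**Working it through.** **Inputs.** Prior means −0.7081 and −0.2619, SD 0.4472, and divisors 25 and 26 (SAP 7.1.2). 20 completers per arm (Protocol 4.3). WM LAR placebo means and residual variances *v* from eight historical studies (Protocol Table 2), with *v* from 0.02191 to 0.31342.

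**The prior centre reproduces the plan's figure.** Placebo mean = −0.7081 − 0.2619 = −0.9700. Attenuation = 1 − 0.7081/0.9700 = 27.0%, the AZ benchmark quoted in SAP 7.1.2. Only the spread is in question.

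**Prior variances.** 0.4472² = 0.19999.

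| | Written | Independent arms |
|---|---|---|
| Var(Intercept) | 0.19999/26 = 0.00769 | 0.00769 |
| Var(Treatment[#1]) | 0.19999 × (1/25 − 1/26) = 0.19999/650 = 0.000308 | 0.19999 × (1/25 + 1/26) = 0.19999 × 51/650 = 0.01569 |
| SD of the difference | 0.0175 L | 0.125 L |
| Prior mean / SD | 0.2619/0.01754 = 14.9 | 0.2619/0.1253 = 2.1 |
| Equivalent subjects per arm (2 × 0.19999/Var) | 1,300 | 25.5 |

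The variance ratio is exactly 51, and the SD ratio is 7.1. The written priors imply a correlation between the arm means of √(25/26) = 0.98.

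**Approximate weight of the trial's data on the difference**, Var/(Var + 2*v*/20):

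| *v* | Written | Independent arms |
|---|---|---|
| 0.022 (lowest) | 12% | 88% |
| 0.130 (df-weighted mean) | 2.3% | 55% |
| 0.313 (highest) | 1.0% | 33% |

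**Posterior probability of any attenuation.** This uses a conjugate bivariate normal model for (Intercept, Treatment[#1]) with 20 per arm and known residual variance. Baseline and centre terms are omitted. Ranges run over the eight studies, each at its own placebo mean and variance.

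| Observed LAR on drug | Written prior | Independent-arm prior |
|---|---|---|
| Same as placebo | > 0.9999 in all eight | 0.75 to 0.96 |
| 50% worse | > 0.9999 in all eight | 0.001 to 0.63 |
| Double placebo | > 0.9999 in all eight | 0.00 to 0.18 |

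With placebo set instead at the unweighted Table 2 mean of −0.656 L, the independent-arm results are 0.76 to 0.95 at no effect and 0.00 to 0.34 at doubling. The written prior still gives more than 0.9999. Gibbs sampling with unknown residual variance, run at three variances for no effect and for 50% worse, also gave 1.0000 under the written prior.

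Even at the lowest variance (placebo mean −0.3749 L), the drug-arm mean would have to reach −2.09 L, 5.6 times placebo, before the probability fell to 0.95. The other seven studies need a larger fall.

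**Model M1.** The flat interaction prior frees the Presumed stratum. At zero observed difference, the check gave 1.0 in Unknown and about 0.50 in Presumed. With LAR doubled and *v* = 0.313, Unknown stays at about 1.000. Presumed gives 0.004 if 10 subjects per arm are in that stratum, 0.032 if 5 and 0.12 if 2. The documents give no split, so these counts are assumptions.

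**The case against.** The strongest reply concerns reach. The analysis is optional and covers one endpoint in one population. The 0.7 success criterion in Protocol 9.2 is not tied to it, and it is not an interim output. The SAP synopsis says: "The principal inferences are expected to come from models with non-informative priors". Table 2.3 reports that unaffected result for the same endpoint, population and visit at higher priority, so headline reviewers would have both. Figure 2.9 overlays the prior and the scaled likelihood, Table 2.5 footnotes the priors and reports posterior SDs and intervals, and SAP 11.11.1 advises plotting each prior. All of this stands and limits the severity. These safeguards may expose the problem, but they do not correct the posterior in Table 2.5. A footnote showing 1/25 − 1/26 also looks like ordinary sample-size arithmetic.

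A second reply is that the SAP does not label 25 and 26 as AZ arm sizes or say that the arms were independent. That reading is an inference. But the printed variance would be right only if the two arm means correlated at about 0.98, and the SAP gives no reason for that.

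A third is that the printed expression evaluates correctly and recovers the placebo-mean variance. This is fair: the fault is a missing prior covariance, not a slip in evaluation. The effect on the treatment difference is the same.

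**Conclusion.** The concern holds. The prior variance of the treatment difference is 51 times too small, assuming 25 and 26 are independent arm sizes. Under M2 and M3, and in the Unknown stratum under M1, the posterior probability of attenuation is then near 1 for any plausible data. The calculations also assume 20 per arm and the variances in Protocol Table 2, and they omit baseline and centre. Those terms would not overturn a prior centred 14.9 SDs from zero.

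The primary analysis and the success criterion are untouched. The SAP should still be corrected before this analysis is run, because as written it cannot serve as a sensitivity analysis.

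**What to change.** Put independent priors on the arm means:

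- active: N(−0.7081, 0.4472²/26)
- placebo: N(−0.9700, 0.4472²/25)

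SAP 3.1 already sets this up for the interim prediction: "a re-parameterized version of Primary analysis Model M3 can be used (Intercept term removed", with a separate prior for each arm. The equivalent in the current parameterisation is a bivariate normal prior on (Intercept, Treatment[#1]) with Var(Treatment[#1]) = 0.4472² × (1/25 + 1/26) and covariance −0.4472²/26.

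Do not only change the minus to a plus. With separate priors, the placebo-mean variance would become 0.00769 + 0.01569 = 0.0234, which is 2.9 times the intended 0.0080.

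Two additions would help. First, note in Table 2.5 that the corrected prior alone gives a 98% probability of benefit (Φ(2.09) = 0.98), so readers can see how much of the posterior comes from AZ. Second, say how the AZ priors apply when exposure is in the model. Under M1 and M2 the Intercept is the active mean in the Unknown stratum, and under M1 the Presumed-stratum difference has no AZ prior.

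The cost is a few lines of SAP text and PROC MCMC code and one table footnote. No new data or subjects are needed.
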